Analyses from this section will utilize p-ERK H-scores from pre-dose, 2-week, 8-week, and 10-week biopsies. Summary statistics (mean, standard deviation, median, minimum, and maximum) will be reported at each time point and for change (actual and percent

changes) from baseline to two weeks in Arm C and for change from 8-week and 10-week in Arms A and B for p-ERK using H-score values.

Depending upon data availability, \log_2 -transformed values of p-ERK H-Score results will be analyzed by analysis of variance (ANOVA) for each cohort. In some cases, it is possible for p-ERK H-Scores to have a value of zero, and if these zero H-Scores are present in the data, we will add an offset of one to all values before conducting any \log_2 -transformations. This analysis will consider time and treatment as the fixed effect, and subject as a random effect. The H-Score calculation at either screening (analysis for combo arm) or week 8 (analysis from monotherapy arms) is the test comparison and the H-Score calculation at either week 2 (analysis for combo arm) or week 10 (analysis from monotherapy arms) is the reference calculation. The analysis will be performed using the mixed linear models procedure within the SAS/STAT module of the SAS system. Point and $(1-2\alpha^*)$ interval estimates of the difference in least-square (LS) means of the test less the reference treatment will be derived using SAS code such as that described below:

```
proc mixed;  
class trt time subject;  
model HScore = time trt;  
random subject;  
lsmeans trt;  
estimate 'B vs. A' trt -1 1 / cl alpha=0.05  
run;
```

(In this code, trt, HScore, and time refer to treatment given, H-Score Value, and the time of H-Score analysis, respectively).

For each primary endpoint, results from these analyses will be exponentiated to obtain point and 90% confidence interval estimates of the appropriate test to reference ratios of geometric least-squares (GLS) means.

Assumptions underlying these analyses will be assessed. If the assumptions are seriously violated, then nonparametric methods will be considered.

The mean and median Intra-tumoral expression levels of ERK over time will be plotted, with treatment highlighted using appropriate graphical techniques (e.g. trellis, plotting symbol, and colour).

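### SAP 11.2.1 specifies a log2 p-ERK model in its text but an untransformed H-Score response in its sample code, and states no base for the back-transformation to a ratio.

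*SAP*

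**What the plan says.** SAP 11.2.1 plans a mixed model for p-ERK H-Score, to be run if the data allow. On the scale, the text says that log2 "transformed values of p-ERK H-Score results will be analyzed by analysis of variance (ANOVA) for each cohort". If any H-Score is zero, "we will add an offset of one to all values before conducting any" log2 step. The estimates "will be derived using SAS code such as that described below", and that code contains "model HScore = time trt". A note under it explains the variables: "In this code, trt, HScore, and time refer to treatment given, H-Score Value, and the time of H-Score analysis, respectively". No line of the code creates a log2 variable.

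After fitting, "results from these analyses will be exponentiated to obtain point and 90% confidence interval estimates" of test-to-reference ratios of geometric least-squares means. No base is given.

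The output goes to Table 5.0040 and, for patients with V600E, to Table 5.0080. Their mock-up (HScore4, SAP 18.2.3) has columns for a ratio estimate and its 90% limits, and no p-value column. The Cox mock-up (HScore5) labels the H-Score decrease as being on the log2 scale.

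**The concern.** The text and the code name different responses for the same analysis. A difference on the log2 scale can be turned into a ratio. A difference in H-Score points cannot, and SAP 11.2 defines the score on a 0 to 300 scale. Even with the response settled, the programmer still has to choose a base. Base 2 undoes log2. Base e does not, yet it is what the SAS EXP function applies and what exponentiating commonly means.

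At stake is the only model-based estimate of p-ERK change in the plan. A raw-scale result would usually be absurd enough to be caught. A base-e result would look like an ordinary ratio and could reach the study report.

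**Working it through.** **The plan's own figures.** The disputed model has no stated figure. SAP 5 gives two p-ERK design figures, both on the percent-change scale, and both reproduce:

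- Half-width with SD 30% and n = 15: t(0.975, 14) × SD/√n = 2.145 × 30/√15 = 16.61%, as stated.
- Power for an 80% reduction with SD 70%: noncentrality (80/70) × √15 = 4.43 on 14 df, giving 0.984, consistent with the stated figure of more than 97%.

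Neither depends on the model in 11.2.1.

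**If the code is followed literally.** The H-Score pairs below are assumed illustrations within the 0 to 300 range. With raw difference d = post − pre, the exponentiated result is 2^d or e^d:

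| Pre to post | True ratio | d | 2^d | e^d |
|---|---|---|---|---|
| 150 to 30 | 0.20 | −120 | 7.5e-37 | 7.7e-53 |
| 150 to 135 | 0.90 | −15 | 3.1e-05 | 3.1e-07 |
| 10 to 9 | 0.90 | −1 | 0.50 | 0.37 |

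The last row shows that at low scores even this route can give a number that looks plausible.

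The raw scale also answers a different question before any exponentiation. Take four patients at 100 before and at 10, 40, 120 and 230 after. The arithmetic mean difference is 400/4 − 100 = 0. The geometric mean ratio is (10 × 40 × 120 × 230)^(1/4)/100 = 0.576.

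**If the log2 response is used.** Let l = log2(r). Then 2^l = r, which is correct. With base e, e^l = r^(1/ln 2) = r^1.44. No assumed data are needed for this:

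| True r | Shown with base e |
|---|---|
| 0.90 | 0.859 |
| 0.80 | 0.72 |
| 0.50 | 0.37 |
| 0.30 | 0.18 |
| 0.20 | 0.098 |

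Confidence limits move by the same rule. An assumed estimate of 0.50 with limits 0.30 and 0.80 would be printed as 0.37 with limits 0.18 and 0.72. Since 1^1.44 = 1, an interval that contains 1 still does. The error exaggerates the size of the change and does not alter which side of 1 the result falls on.

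**Effect of the offset.** With one added to every value, the ratio is of H-Score + 1: 150 to 30 gives 31/151 = 0.205, and 10 to 9 gives 10/11 = 0.909.

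**The case against.** The best defence is that the code is only an example, introduced as such. It names no dataset, and SAP 9.2 places full derivations and transformations in separate dataset specifications. The text fixes the scale, the offset rule and the target, and both mock-ups agree with it. On that view HScore may simply hold the log2 value, and base 2 is the natural inverse. A programmer who reads it this way gets the right scale. That much stands. It means that a wrong ratio is not inevitable, and that base e is a risk left open by silence, not an instruction.

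It does not remove the contradiction. The SAP goes out of its way to gloss the response as the H-Score value, which points to the raw score. Calling the code an example does not supply the missing base.

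A reader might also infer that the model tests the wrong null hypothesis and loses power on the raw scale. The documents do not support that. Protocol 9.1 and SAP 2.3 and 11 say that the primary endpoint is descriptive with no hypothesis test, and the mock-up for this model has no p-value.

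**Conclusion.** The contradiction is real and worth correcting before programming. Its size depends on what the programmer does:

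- Log2 response with base 2: no error.
- Log2 response with base e: every ratio and limit becomes its 1.44th power, overstating suppression in Tables 5.0040 and 5.0080.
- Raw response, then exponentiated: the output is not a ratio at all.

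The issue is confined to this estimate and its interval. One might infer that the primary endpoint is compromised, but it is percentage change in p-ERK score. The actual and percent-change summaries in 11.2.1 (Tables 5.0030 and 5.0031) are computed without the model. The r^1.44 figures are pure arithmetic; the H-Score pairs and the example interval are assumptions, because the documents give no H-Score data.

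**What to change.** In SAP 11.2.1:

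1. Derive `LHSCORE = log2(H-Score)`, or `log2(H-Score + 1)` for all values if any zero occurs. This keeps the SAP's existing conditional offset.
2. Use `model LHSCORE = ...` in the code, and correct the note that explains the variables.
3. Replace the instruction to exponentiate with: back-transformed as `2**estimate`, `2**lower` and `2**upper`.
4. Footnote Tables 5.0040 and 5.0080 to say that the ratio is of H-Score + 1 when the offset applies.

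The cost is a few lines of wording and code, with no new data.

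These edits settle the scale only. Three separate mismatches in the same block should be resolved when it is opened:

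- The code's alpha=0.05 gives a 95% interval where the text and mock-up say 90% (t multiplier 2.145 against 1.761 at 14 df, 22% wider).
- The text takes the earlier biopsy as test and the later one as reference, the reverse of the mock-up's B versus A.
- If the model is fitted within one arm at two time points, treatment and time coincide, so the treatment contrast cannot be estimated.

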11.2. Investigator Assessment of H-Score

The primary endpoint analysis will be the evaluation of the percentage change of the mean Phosphorylated Extracellular Signal-regulated Kinase (p-ERK) H-Score from baseline. At the beginning of IP treatment, the p-ERK H-Score will be determined for all participants in the biomarker population.

Change in biomarker status is most prominent within two weeks of start of treatment. Patients from arm A and arm B will be given combination therapy starting from week 9 after completion of 8 weeks of monotherapy. Therefore, changes in biomarker between screening and week 2 as well as between week 8 and week 10 will be summarized and listed. All visits for biomarker samples have a window of ± 7 days.

More specifically, the procedure for calculating the p-ERK score is shown below:

- Intra-tumoral expression levels of ERK, a tumor tissue biomarker, will be measured using immunohistochemistry methods that incorporated both intensity and distribution of staining. A value designated the H-Score will be derived by summing the percentages of cells staining at each intensity multiplied by the weighted intensity of staining (0, 1+, 2+, 3+: 3+ indicates the strongest staining, 2+ indicates medium staining, 1+ indicates weak staining, and 0 indicates no staining). H-Scores range from a minimum score of 0 to a maximum score of 300; the maximum score indicates the strongest expression. We will also collect a summary staining score for the tumor tissue which has potential values of 0 (no staining), 1+ (weak staining), 2+ (medium staining), and 3+ (strong staining).

$$\begin{aligned}
 H - Score &= (3 * \% \text{ Cells with strongest staining}) \\
 &\quad + (2 * \% \text{ Cells with medium staining}) \\
 &\quad + (1 * \% \text{ Cells with weak staining}) \\
 &\quad + (0 * \% \text{ Cells with no staining}) \uparrow
 \end{aligned}$$

All p-ERK H-Score data will be recorded on the eCRF, including data on % positivity for all participants in the biomarker population, which is calculated using the equation below:

$$\begin{aligned}
 \% \text{ Positivity} &= \% \text{ of cells with weak staining} \\
 &\quad + \% \text{ of cells with medium staining} \\
 &\quad + \% \text{ of cells with strong staining} \uparrow
 \end{aligned}$$

Summary statistics, graphics, and statistical modeling will be conducted on the biomarker population for each arm of the study.

11.2.1. Primary p-ERK Biomarker Analyses:

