Treatment Arm	Comparison	N	LS Mean Num.	LS Mean Demon.	Ratio Estimate	Lower 90% Confidence Limit	Upper 90% Confidence Limit
GSK2118436 BID 8W then GSK1120212 QD + GSK2118436 BID	B vs A						
GSK1120212 QD 8W then GSK1120212 QD + GSK2118436 BID	B vs A						
GSK1120212 QD + GSK2118436 BID	B vs A						

Comparison for H-Score Times: B = Combo Therapy and A = Monotherapy or No Therapy (for Cohort that has Combination Therapy at start of study)

Example HScore5
Protocol: IMM123456
Population: Safety

Page 1 of x

Table X
Multivariate Proportional Cox Model Examining the relationship between
H-Score and Progression Free Survival/Duration of Response

Parameter	Parameter Estimate	P-Value	HR	Low 95% CI	High 95% CI
Decrease in H-Score (Log 2 Scale)					
Age					
Sex					
ECOG Status					
Initial Combo therapy					
V600E Status					

Example HScore6
 Protocol: BRF116613
 Population: Biomarker

Table X
 Correlation of Changes in H-Score after Two Weeks of Combo Therapy and Changes in Tumor Burden

Clinical Marker of Interest	Treatment Arm	Spearman's Coefficient	N
% Change in Sum of Lesion Diameters	GSK2118436 BID 8W then GSK1120212 QD + GSK2118436 BID		
% Change in Sum of Lesion Diameters	GSK1120212 QD 8W then GSK1120212 QD + GSK2118436 BID		
% Change in Sum of Lesion Diameters	GSK1120212 QD + GSK2118436 BID		

Example HScore7
 Protocol: XYZ100001
 Population: Intent-to-Treat/Safety/Other study specific

Table X
 Summary of Investigator/Independent Reviewer/etc.-Assessed Best Response (without or with confirmation)
per baseline H-Score Category (RECIST 1.1 Criteria)

	Treatment A (N=300)	Treatment B (N=200)	Treatment C (N=200)	Total (N = 54)
p-ERK IHC H-Score btw. 200-300				
Complete Response	22 (7%)	10 (5%)	10 (5%)	
Partial Response	30 (10%)	40 (20%)	50 (25%)	
Stable Disease	153 (50%)	110 (55%)	100 (50%)	
Non-CR/Non-PD	3 (1%)	0	0	
Progressive Disease	70 (23%)	33 (17%)	33 (17%)	
Not Evaluable	25 (9%)	7 (3%)	7 (3%)	

Response Rate

CONFIDENTIAL

BRF116613

CR+PR	52 (17.3%)	50 (25.0%)	60 (30.0%)
95% Confidence Interval	(13.2%, 22.1%)	(19.2%, 31.6%)	(23.7%, 36.9%)
p-ERK IHC H-Score btw. 100-200			
Complete Response	22 (7%)	10 (5%)	10 (5%)
Partial Response	30 (10%)	40 (20%)	50 (25%)
Stable Disease	153 (50%)	110 (55%)	100 (50%)
Non-CR/Non-PD	3 (1%)	0	0
Progressive Disease	70 (23%)	33 (17%)	33 (17%)
Not Evaluable	25 (9%)	7 (3%)	7 (3%)
Response Rate			
CR+PR	52 (17.3%)	50 (25.0%)	60 (30.0%)
95% Confidence Interval	(13.2%, 22.1%)	(19.2%, 31.6%)	(23.7%, 36.9%)

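### The per-arm p-ERK mixed model fits visit and treatment given together, so its ratio and LS means cannot be estimated on the planned schedule; its confidence level and ratio direction also conflict with its own table shell

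*SAP*

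**What the plan says.** SAP 11.2.1 plans, if the data allow, an analysis of variance of log2 H-scores for each cohort: "This analysis will consider time and treatment as the fixed effect, and subject as a random effect". The sample PROC MIXED code follows the text with "model HScore = time trt", a random subject effect, `lsmeans trt`, and "estimate 'B vs. A' trt -1 1 / cl alpha=0.05". The variables are then defined: "In this code, trt, HScore, and time refer to treatment given, H-Score Value, and the time of H-Score analysis, respectively".

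On timing, SAP 11.2 states: "Patients from arm A and arm B will be given combination therapy starting from week 9 after completion of 8 weeks of monotherapy". Arm C receives the combination from the start.

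On the interval, the text says "results from these analyses will be exponentiated to obtain point and 90% confidence interval estimates" of test-to-reference ratios. On direction, it says of the screening score (Arm C) or Week 8 score (Arms A and B) that it "is the test comparison and the H-Score calculation at either week 2 (analysis for combo arm) or week 10" (the latter for the monotherapy arms) is the reference. The difference taken is test less reference.

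The output is mock-up HScore4 in SAP 18.2.3, used for Tables 5.0040 and 5.0080. It has one row per arm, with numerator and denominator LS means, a ratio, and limits headed "Lower 90% Confidence Limit" and the matching upper limit. Its comparison is B vs A, where B is combination therapy and A is monotherapy or, in Arm C, no therapy.

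**The concern.** Within one arm, treatment given follows from the visit. Arms A and B are on monotherapy at Weeks 2 and 8 and on the combination at Week 10. Arm C is untreated at screening and on the combination afterwards. A model containing both factors cannot say how much of the Week 8 to Week 10 change belongs to time and how much to treatment, yet HScore4 asks for the treatment part alone.

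On a fully on-schedule data set SAS would report the estimates as non-estimable, so the failure would be visible, but the model would have to be respecified after the data are in hand. The less visible risk is a data set with a few off-schedule patients: a ratio prints, looks normal, and is not the visit-to-visit change that the table names. Separately, a programmer working from the code would put 95% limits under 90% headings, and one working from the text would invert the ratio.

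**Working it through.** **Inputs.** The model terms, the definition of `trt`, the contrast and the visits (pre-dose, Weeks 2, 8 and 10) come from SAP 11.2.1. Treatment by visit comes from SAP 3 and 11.2. The figure of 15 evaluable patients per arm comes from SAP 5.1.

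**1. Estimability on the planned schedule.** Take Arm A or B at Weeks 8 and 10, with time effects τ and treatment effects θ:

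- Week 8 mean = μ + τ8 + θA
- Week 10 mean = μ + τ10 + θB
- Difference = (τ10 − τ8) + (θB − θA)

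The data fix only this sum. The code asks for θB − θA alone. Any constant can be moved from τ10 to θB without changing a fitted value. In one simulated arm with a paired log2 change of −0.92, two solutions with identical fitted values gave treatment contrasts of 0 and −0.46.

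The formal test is that a vector L is estimable only if rank([X; L]) = rank(X). X holds the intercept, time and treatment columns. For the contrast, L = θB − θA. For an LS mean, L = intercept + average of the time effects + one treatment level.

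| Design, 15 patients | Rank of X | Rank, time alone | Contrast | LS means |
|---|---|---|---|---|
| A/B, Weeks 8 and 10 | 2 | 2 | not estimable | not estimable |
| C, screening and Week 2 | 2 | 2 | not estimable | not estimable |
| A/B, four visits | 4 | 4 | not estimable | not estimable |
| C, four visits | 4 | 4 | not estimable | not estimable |
| A/B, Weeks 8 and 10, one early switcher | 3 | 2 | estimable | estimable |
| One factor only, two planned visits | 2 | – | estimable | estimable |

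Other readings do not help. If `trt` means assigned arm, it is constant within a cohort. Pooling the arms makes monotherapy versus combination estimable, but not none versus combination or any LS mean. It also departs from the per-cohort model and HScore4's one row per arm.

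**2. Off-schedule dosing.** Early switching (SAP 3), interrupted dosing with visits kept on calendar (Protocol 5.8.2 Table 5; Table 19 footnote 1) and continuing on one drug (Protocol 4.2.1) can break the collinearity if `trt` is coded from actual dosing at each visit. As an illustration in Arm A or B, let 14 patients fall from 100 to 20 (ratio 0.20) and let one early switcher, on the combination at both visits, score w at Week 8 and 20 at Week 10. The switcher alone identifies the time effect, 20/w, so the treatment ratio is 0.20 ÷ (20/w). The time-only ratio is the geometric mean change, (0.20¹⁴ × 20/w)^(1/15).

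| w | Treatment ratio, SAP model | Time-only ratio |
|---|---|---|
| 20 | 0.20 | 0.22 |
| 50 | 0.50 | 0.21 |
| 100 | 1.00 | 0.20 |

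In Arm C, let one patient be off drug at Week 2, scoring 100 at screening and 100, 50 or 20 at Week 2. The treatment ratio is then 0.20, 0.40 or 1.00, and the time-only ratio 0.22, 0.21 or 0.20. In both examples the ratios are the same for any intraclass correlation (ICC).

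The standard error relative to the plain change, √(2(1−ICC)/15) in residual-SD units, with one such patient, is:

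- ICC near 1: √(15 × (1/14 + 1)) = 4.0
- ICC 0: √(7.5 × (1/14 + 1)) = 2.8

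With four such patients the range is 1.6 to 2.3.

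**3. Confidence level.** The text's general form, 1 − 2α, gives 90% at α = 0.05, which agrees with its stated 90% and with HScore4. In PROC MIXED, `cl alpha=0.05` gives 1 − 0.05 = 95%. With 14 df, t is 1.761 for 90% and 2.145 for 95%. The ratio 1.761/2.145 = 0.82, so the intended interval is 18% narrower on the log scale.

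**4. Direction.** For an 80% fall, the text (before ÷ after) gives 1/0.20 = 5.0. HScore4 (combination ÷ mono or none) gives 0.20.

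**The case against.** The strongest reply is that the intent is recoverable and little depends on it. The text names the two visits for each arm, and HScore4 fixes direction, level and layout. The code is offered only as an example, the model is fitted only if the data allow, and the endpoint is descriptive. Tables 5.0030 and 5.0031 and the sample size do not use it. All of this stands and limits the severity. It does not rescue the model, because the text as well as the code specifies both factors.

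A second reply is that the off-schedule figures need `trt` to be recoded visit by visit from actual dosing. HScore4 can be read as tying A and B to visits, and data are reported by nominal visit (SAP 9.2.9 and 9.3). Under that coding the model simply fails and no misleading number appears. Coding an interrupted Arm C patient as untreated at Week 2 is nowhere stated, and the scores are invented. The figures are indeed conditional on that coding. But SAP 11.2.1 itself defines `trt` as treatment given. SAP 9.2.9 and 9.3 govern which visit a value belongs to, and SAP 9.2.10 governs a subject-level treatment label; none of them settles the coding at a visit. Either reading leaves the table without the intended estimate.

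Third, the code says only B vs. A, and the sign of `-1 1` depends on how the levels sort. That is correct: the code agrees with HScore4 through HScore4's definition of B and A, and only if A sorts first. The contradiction between the text and HScore4 is unaffected.

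**Conclusion.** The specification is wrong as written. On the planned schedule the treatment contrast and both treatment LS means are non-estimable in all three arms, whether two or four visits are used, so the estimate columns of Tables 5.0040 and 5.0080 cannot be produced. This rests only on the stated model and the planned treatment by visit.

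If treatment is coded from actual dosing, a few off-schedule patients make the contrast estimable but determine its value. The ratios and standard-error multiples above illustrate this; the documents give no expected number of such patients.

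The 95% versus 90% level and the reversed ratio are plain contradictions, and HScore4's headings show what was meant. The point should be fixed, but it does not threaten the descriptive p-ERK summaries or the sample size.

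**What to change.** In SAP 11.2.1, for each arm:

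- Use only the two planned visits: Weeks 8 and 10 in Arms A and B, screening and Week 2 in Arm C.
- Keep one fixed factor, for example time, with subject random. With complete pairs the estimate equals the mean paired log2 change.
- Estimate post- minus pre-combination, and take the LS means from the same factor so that HScore4's columns can be filled.
- Set `alpha=0.10` to match the 90% in the text and HScore4.
- Reword the text so that the post-combination score is the test and the pre-combination score the reference.

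How patients who are off schedule at these visits are handled in the analysis is a separate choice, which the SAP should state.

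The cost is a few lines of SAP text and code, with no effect on data collection, patients or sample size.

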# 1.1.2. The MEK Inhibitor Trametinib as Monotherapy

Trametinib is a reversible, highly selective allosteric inhibitor of MEK1/2 activation and kinase activity. A Phase 3 trial, METRIC (MEK114267), was conducted in patients with BRAF V600E/K mutation positive advanced or metastatic melanoma. Patients were randomised 2:1 to trametinib (2mg once daily) or chemotherapy (DTIC or paclitaxel). Patients were stratified by baseline LDH level and prior chemotherapy; patients in the chemotherapy arm were allowed to crossover to receive trametinib after confirmation of PD. The primary endpoint was PFS in patients with BRAF V600E mutation-positive metastatic melanoma and no prior brain metastases; PFS was also evaluated in the ITT

population. Secondary endpoints were OS, ORR in the primary and ITT population and safety in the safety population (Flaherty, 2012b).

Three hundred and twenty-two patients were randomised to trametinib (n=214) or chemotherapy (n=108); 273 patients were BRAF V600E mutation-positive with no prior brain metastases. Median age was 54 years; all had an ECOG performance status of 0 (64%) or 1 (36%), and 65% were M1c (Flaherty, 2012b).

The HR for the primary population for PFS by investigator was 0.44 (95% CI 0.31–0.64; p<0.0001) in favour of trametinib with a median PFS of 4.8 months vs. 1.4 months with chemotherapy. The confirmed ORR was 24% with trametinib and 7% with chemotherapy. HR for interim OS was 0.53 (95% CI 0.30–0.94; p=0.0181), in favour of trametinib.

The most frequent AEs ( $\geq$ 20%) with trametinib were skin rash (57%), diarrhoea (43%), fatigue (26%), and oedema (26%). Known MEK inhibitor class effects were observed in this study including chorioretinopathy (<1%) and decreased ejection fraction (7%).

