For further exploratory purposes and if data warrant, multivariate proportional Cox models examining the relationships between PFS and DoR and decreases in H-Score from none or mono therapy to combo therapy may be examined with age, sex, ECOG status, initial drug exposure (combo therapy vs. monotherapy), and BRAF mutation type (V600E vs. V600K) as potential covariates using backward selection. If multivariate proportional Cox models are developed, a listing containing the values for each variable as part of the Cox model will be created.

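### The exploratory Cox models let backward selection remove the only treatment term, so the p-ERK hazard ratio can take up part of an arm effect

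*SAP*

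**What the plan says.** The last paragraph of SAP 11.2.1 opens "For further exploratory purposes and if data warrant, multivariate proportional Cox models". These models relate PFS and DoR to a single predictor, "decreases in H-Score from none or mono therapy to combo therapy". Earlier in the same section the summaries of change are set out "from baseline to two weeks in Arm C and for change from 8-week and 10-week in Arms A and B".

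Age, sex and ECOG status, together with "initial drug exposure (combo therapy vs. monotherapy), and BRAF mutation type (V600E vs. V600K) as potential covariates using backward selection", complete the model. No term is forced in, there is no stratification by arm and no arm-by-decrease term, and no significance level for staying in the model is given.

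The results go to Tables 5.0050 (PFS) and 5.0051 (DoR), and to Tables 5.0090 and 5.0091 for patients with V600E. Their common shell, HScore5 in SAP 18.2.3, has one row for the H-Score decrease on the log2 scale and one row for initial combination therapy, each with a p-value, hazard ratio and 95% CI. It has no column or row by arm.

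**The concern.** In Arm C the predictor is the drop from no drug to two drugs. In Arms A and B it is the further drop from one drug to two, after eight weeks of pathway inhibition. The two quantities share a name but not a reference state or a time window, so their means may well differ between Arm C and the other arms. If PFS or DoR also differs, treatment confounds the link between H-Score decrease and outcome. Only the initial-exposure term protects against this, and backward selection may delete it. In a small data set, deletion mostly reflects low power and does not show that the arms are alike.

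These four tables are the only listed displays that link p-ERK to PFS or DoR, and they print a p-value beside the H-Score row. A reader could take a difference between treatment sequences as evidence that p-ERK itself predicts outcome.

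**Working it through.** **The plan's own figures.** The SAP gives no event count or power for the Cox models. Its sample-size figures (SAP 5.1 and 5.2) reproduce. The half-width is t(0.975, 14) × SD/√15 = 2.145 × 30/3.873 = 16.61. The paired t-test for an 80% reduction with SD 70% and n = 15 has 98.4% power, in line with the stated >97%. The point below does not depend on these.

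**Can the term survive selection?** Approximate power for a two-level term with one third of patients in Arm C is Φ(|ln HR| × √(d × 1/3 × 2/3) − 1.96), where d is the number of events. For d = 30 and HR 0.6 this is Φ(0.511 × 2.582 − 1.96) = Φ(−0.64) = 26%.

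| Events | HR 0.5 | HR 0.6 | HR 0.7 |
|---|---|---|---|
| 20 | 31% | 19% | 11% |
| 30 | 43% | 26% | 15% |

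A real arm effect of this size would therefore usually be removed at the 0.05 level.

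**What follows when it is removed?** Two sets of simulations were run with no p-ERK effect within any arm and the H-Score term always kept. The arm hazard ratio, the gap in mean log2 decrease, its SD, the accrual or censoring pattern and the stay level are all assumptions, because the documents give none of them.

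*Set 1:* 15 per arm, SD 1, median PFS 7 months in Arms A/B, uniform censoring at 4 to 18 months, stay level 0.05, about 1,000 trials per row.

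| Arm HR | Gap | Events | Term dropped | p-ERK HR when dropped | False positives, backward selection | False positives, term forced in |
|---|---|---|---|---|---|---|
| 1.0 | 1.8 | 29 | 92.6% | 1.00 | 6.8% | 5.5% |
| 0.7 | 0 | 27 | 87.8% | 1.00 | 7.3% | 5.5% |
| 0.7 | 1.0 | 27 | 87.3% | 0.92 | 8.1% | 5.7% |
| 0.7 | 1.8 | 27 | 89.5% | 0.91 | 11.7% | 6.2% |
| 0.6 | 1.8 | 26 | 87.4% | 0.88 | 12.4% | 4.4% |
| 0.5 | 0 | 25 | 72.5% | 0.99 | 7.8% | 5.9% |
| 0.5 | 1.8 | 25 | 75.4% | 0.84 | 17.4% | 6.6% |

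Adding a stay level of 0.10 and 18 per arm (up to 34 events), scenarios with an arm HR of 0.5 to 0.7 and a gap of 1.0 to 1.8 give: term dropped in 62% to 90%, false positives 8% to 18%, and 4% to 7% with the term forced in.

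*Set 2:* 14 per arm, SD 1.5, median PFS 7.4 months in Arms A/B (the pooled combination figure in Protocol 1.1.3), 12-month accrual, stay level 0.05, about 21 to 22 events at arm HRs of 0.6 and 0.45. There were 1,200 trials per scenario for those two HRs and 1,000 for the other rows.

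| Arm HR | Gap 1 | Gap 2 | Gap 3 | Stratified by arm |
|---|---|---|---|---|
| 1.0 | 6.8% | 8.8% | 7.9% | – |
| 0.69 | 7.2% | 9.6% | 11.2% | – |
| 0.6 | 8.3% | 12.2% | 12.6% | 4.2%, 4.8%, 4.4% |
| 0.45 | 10.7% | 14.0% | 19.3% | about 5% |

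A repeat of the HR 0.6 row gave 7.9%, 11.2% and 14.3%. The Monte Carlo standard error at 8% with 1,000 trials is √(0.08 × 0.92/1000) = 0.9 points.

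**How much of the arm effect is taken up?** If the p-ERK slope carried all of it, an arm HR of 0.5 across a gap of 1.8 would give 0.5^(1/1.8) = 0.68 per log2 unit. The simulated value when the term is dropped is 0.84, and ln 0.84/ln 0.68 = 0.174/0.385 = 0.45. A linear approximation agrees: the between-arm share of the predictor's variance is (2/9 × 1.8²)/(2/9 × 1.8² + 1²) = 0.72/1.72 = 0.42. For a gap of 1.0 it is 0.222/1.222 = 0.18.

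**The case against.** Several counter-arguments have force. The models are optional, PFS and DoR are themselves exploratory, and SAP 2.3 plans no hypothesis test. Selection alone raises the error rate: with no arm effect, Set 2 gives 6.8% to 8.8%. At the smallest gap and mildest arm effect (7.2%), the excess is therefore almost entirely selection noise. The stronger arm effects also imply Arm C medians of 7.4/0.6 = 12.3 and 7.4/0.45 = 16.4 months, above the 10.8 months that Protocol 1.1.3 reports for the 150/2 cohort; 7.4/10.8 gives about 0.69. DoR, which is limited to responders, was not simulated. All of this limits the size of the problem; none of it removes the mechanism.

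Two passages might seem to settle the matter. SAP 11.2 says "statistical modeling will be conducted on the biomarker population for each arm of the study", but a combination-versus-monotherapy covariate is constant within an arm, so this model can only be fitted to pooled arms. HScore5 does have a row for initial combination therapy, but it lists every candidate and does not say that the term is retained.

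A reader might infer that any arm difference in PFS or DoR would be reported as a p-ERK effect, or that the arm largely determines the H-Score decrease. The documents support neither: they give no between-arm gap or log2 SD, and the calculation shows only partial uptake. A reader might also conclude that LDH or stage must be added because, in a cited Phase III trial, "Patients were stratified by baseline LDH level and prior chemotherapy". That describes another trial's randomisation. Adding these covariates here is a matter of preference and was not tested.

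**Conclusion.** The concern holds as a conditional weakness of the exploratory Cox models. Three things must coincide: the arms differ in PFS or DoR, the mean H-Score decrease differs between Arm C and Arms A/B, and the exposure term is dropped. The third is likely at about 20 to 34 events. The p-ERK hazard ratio then takes up part of the arm effect, with a mean of 0.84 to 0.94 per log2 unit in Set 1 when the true value is 1. Overall PFS false-positive rates are roughly 8% to 19%, against about 4% to 7% when treatment is kept, and part of the excess at the low end is ordinary selection noise. These sizes rest on assumed arm HRs of 0.45 to 0.7, gaps of 1 to 3 log2 units and assumed event counts. For DoR the mechanism is the same but its size is unknown. With no arm effect or no gap, the p-ERK hazard ratio stays near 1. The primary descriptive p-ERK endpoint is not affected.

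**What to change.** In SAP 11.2.1, take treatment out of backward selection by stratifying the Cox models by the three randomised arms. At minimum, force in either a three-level arm term or the existing initial-exposure term. Forcing in the existing term brought false positives to about 4% to 7%, close to stratification, but it still merges Arms A and B.

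Stratification leaves one common H-Score coefficient for decreases that have different reference states. Tables 5.0050 and 5.0051 should therefore also show the H-Score hazard ratio separately for Arm C and for Arms A/B, as a descriptive line only: at about 21 events in total, an even split would leave about 21/3 = 7 per arm. Apply the same to Tables 5.0090 and 5.0091.

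The cost is one SAP paragraph and extra shell rows, a somewhat wider CI for the H-Score term, and the loss of between-arm information on p-ERK.
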